7.0 REGISTRATION PROCEDURES

7.1 General Guidelines

Prior to registration and any study-specific evaluations being performed, all patients must have given written informed consent for the study and must have completed the pre-treatment evaluations. Patients must meet all of the eligibility requirements listed in Section 3. Eligible patients will be entered on study centrally by the University of Chicago multi-site coordinator. All sites should call the coordinator at [contact] or [contact] to verify availability of a slot.

7.2 Registration Process

When a potential patient has been identified, notify the CRA via phone or email to ensure a reservation on the study ([contact] or [contact]). Reservations for potential subjects will only be held for subjects who have signed consent for that particular study.

When registering a subject, the following must occur:

- Confirm that the institution has a current IRB approval letter for the correct version of protocol/consent and has an annual update on file, if appropriate.
- Submit all required materials (Eligibility Checklist, Source documentation, & signed consent form) to confirm eligibility and required pre-study procedures to the CRA a minimum of 48 hours prior to the subject's scheduled therapy start date.
- Source documentation includes copies of all original documents that support each inclusion/exclusion criteria. The eligibility checklist does not serve as source documentation but rather as a checklist that original source documentation exists for each criterion.
- Communicate with the CRA to ensure all necessary supporting source documents are received and the potential subject is eligible to start treatment on schedule. If there are questions about eligibility, the CRA will discuss it with the PI. PI may clarify, but not overturn, eligibility criteria.
- Affiliate sites must confirm registration of subjects by obtaining a subject study ID number from the CRA via phone, fax or email.
- If a subject does not start on the scheduled day 1 treatment date, promptly inform the CRA as the delay in start may deem the subject ineligible and/or require further or repeat testing to ensure eligibility.
- The date the patient receives treatment for the first time will be considered the patient's "OnStudy Date." The patient's subject ID will be assigned and a confirmation of registration will be issued by the CRA on this date. Subjects that sign consent and do not go "OnStudy" will be recorded in the database with the date they signed consent

Protocol Version: 04/10/2019

Page 36 of 72

and the reason for not going "OnStudy" (e.g., Ineligible, Screen Failure or Withdrawn Consent).

8.0 TRIAL PROCEDURES

8.1 Trial Procedures

The Trial Flow Chart - Section 6.0 summarizes the trial procedures to be performed at each visit. Individual trial procedures are described in detail below. It may be necessary to perform these procedures at unscheduled time points if deemed clinically necessary by the treating investigator.

Furthermore, additional evaluations/testing may be deemed necessary by the investigator for reasons related to subject safety. In some cases, such evaluation/testing may be potentially sensitive in nature (e.g., HIV, Hepatitis C, etc.), and thus local regulations may require that additional informed consent be obtained from the subject. In these cases, such evaluations/testing will be performed in accordance with those regulations.

8.1.1 Administrative Procedures

8.1.1.1 Informed Consent

The Investigator must obtain documented consent from each potential subject prior to participating in a clinical trial.

8.1.1.1.1 General Informed Consent

Consent must be documented by the subject's dated signature or by the subject's legally acceptable representative's dated signature on a consent form along with the dated signature of the person conducting the consent discussion.

A copy of the signed and dated consent form should be given to the subject before participation in the trial.

The initial informed consent form, any subsequent revised written informed consent form and any written information provided to the subject must receive the IRB/ERC's approval/favorable opinion in advance of use. The subject or his/her legally acceptable representative should be informed in a timely manner if new information becomes available that may be relevant to the subject's willingness to continue participation in the trial. The communication of this information will be provided and documented via a revised consent form or addendum to the original consent form that captures the subject's dated signature or by the subject's legally acceptable representative's dated signature.

Specifics about a trial and the trial population will be added to the consent form template at the protocol level.

The informed consent will adhere to IRB/ERC requirements, applicable laws and local regulations.

8.1.1.2 Inclusion/Exclusion Criteria

All inclusion and exclusion criteria will be reviewed by the investigator or qualified designee to ensure that the subject qualifies for the trial.

8.1.1.3 Medical History

A medical history will be obtained by the investigator or qualified designee. Medical history will include all active conditions, and any condition diagnosed within the prior 10 years that are considered to be clinically significant by the Investigator. Details regarding the disease for which the subject has enrolled in this study will be recorded separately and not listed as medical history.

8.1.1.4 Prior and Concomitant Medications Review

8.1.1.4.1 Prior Medications

The investigator or qualified designee will review prior medication use, including any protocol-specified washout requirement, and record prior medication taken by the subject within 28 days before starting the trial. Treatment for the disease for which the subject has enrolled in this study will be recorded separately and not listed as a prior medication.

8.1.1.4.2 Concomitant Medications

The investigator or qualified designee will record medication, if any, taken by the subject during the trial. All medications related to reportable SAEs and ECIs should be recorded.

8.1.1.5 Disease Details and Treatments

8.1.1.5.1 Disease Details

The investigator or qualified designee will obtain prior and current details regarding disease status.

8.1.1.5.2 Prior Treatment Details

The investigator or qualified designee will review all prior cancer treatments including systemic treatments, radiation and surgeries.

8.1.1.5.3 Subsequent Anti-Cancer Therapy Status

The investigator or qualified designee will review all new anti-neoplastic therapy initiated after the last dose of trial treatment. If a subject initiates a new anti-cancer therapy within 30 days after the last dose of trial treatment, the 30 day Safety Follow-up visit must occur before the first dose of the new therapy. Once new anti-cancer therapy has been initiated the subject will move into survival follow-up.

Protocol Version: 04/10/2019

Page 38 of 72

8.1.1.6 Adverse Event (AE) Monitoring

The investigator or qualified designee will assess each subject to evaluate for potential new or worsening AEs as specified in the Trial Flow Chart and more frequently if clinically indicated. Adverse experiences will be graded and recorded throughout the study and during the follow-up period according to NCI CTCAE Version 5 (see Section 11.2). Toxicities will be characterized in terms regarding seriousness, causality, toxicity grading, and action taken with regard to trial treatment.

8.1.1.7 Physical Exam

The investigator or qualified designee will perform a physical exam at protocol specified time points as per the Trial Flow Chart (Section 6.0). Clinically significant abnormal findings should be recorded as medical history. A full physical exam should be performed during screening.

8.1.1.8 Vital Signs

The investigator or qualified designee will take vital signs at screening, prior to the administration of each dose of trial treatment and at treatment discontinuation as specified in the Trial Flow Chart (Section 6.0). Vital signs should include temperature, pulse, respiratory rate, weight and blood pressure. Height will be measured at screening only.

8.1.1.9 Eastern Cooperative Oncology Group (ECOG) Performance Scale

The investigator or qualified designee will assess ECOG status at screening, prior to the administration of each dose of trial treatment and discontinuation of trial treatment as specified in the Trial Flow Chart.

8.1.1.10 Tumor Imaging and Assessment of Disease

Baseline and restaging radiologic imaging will be performed to encompass all sites of metastatic disease. This will generally include at least CT CAP though the specific imaging study can be changed by the treating investigator depending on patient circumstances. Radiologic imaging modality should be consistent throughout the study for response assessment. For patients who have known bone metastases at baseline, bone scan should additionally be pursued as standard of care for disease assessment.

8.1.1.11 Tumor Tissue Collection and Correlative Studies Blood Sampling

The following tables outline the requirements for tissue and blood banking. These will be collected and stored for batched future analysis.

Biospecimen type	Collection Time Point	Number of
		samples per
		patient

Protocol Version: 04/10/2019

Page 39 of 72

Fecal sample	Pre administration of EDP1503	10 samples (2 samples each from
	Following run in of EDP1503	5 time points)
	At dose 4 of treatment with pembrolizumab	
	At discontinuation visit	
	30 days after cessation of EDP1503	
A paraffin-embedded tissue block of metastatic tumor taken before initiation of treatment.	Pre-treatment: obtained prior treatment on protocol	1 historical sample
Paraffin-embedded tissue block of metastatic tumor taken before initiation of treatment (if available).	Pre-treatment: obtained prior treatment on protocol	1 sample
Paraffin-embedded tissue block of metastatic tumor taken after EDP1503 run in. Where feasible this should be taken from the same metastatic or primary site as the initial biopsy.	Pre-treatment: obtained after the EDP1503 run in	1 sample
Peripheral Blood Mononuclear Cells: ~60 ml of anti-coagulated whole blood in green top tube	Pre-administration of EDP1503: 8-10 tubes taken within 21 days prior to EDP1503 administration. 8-10 tubes taken at the	Up to 40 samples total over 4 time points
	following time points:	
	(1) at day of dose 1 pre- administration of pembrolizumab	
	(2) dose 4 pembrolizumab	
	(3) at time of progressive disease.	
Whole blood for germline DNA: 8-10 mL of whole blood in PAXgene tube	Within 21 days prior to administration of EDP1503	1 sample
Cytokines	Pre administration of EDP1503	4 samples

Protocol Version: 04/10/2019 Page 40 of 72

	Following approximately 48 hours of EDP1503	
	Following run in of EDP1503	
	At dose 4 of treatment with pembrolizumab	
Blood Culture	Pre administration of EDP1503	2 samples
	Following run in of EDP1503	
EDP1503 PCR	Pre administration of EDP1503	2 samples
	Following run in of EDP1503	

Biospecimens will be shipped and stored in the University of Chicago Human Immune Monitoring Core Facility as below with the exception of one stool sample from each time point which will be sent to Evelo Biosciences.

Human Immune Monitoring Core:

Contact: [name] University of Chicago - Human Immune Monitoring Core [name]

[contact] [contact]

Ship human microbiome sample kits to*:

8.1.2 Laboratory Procedures/Assessments

Laboratory tests for hematology, chemistry, urinalysis, and others are specified in Table 5.

Laboratory tests for screening or entry into the Second Course Phase should be performed within 14 days prior to EDP1503 administration. After Cycle 1, pre-dose laboratory procedures can be conducted up to 72 hours prior to dosing. Results must be reviewed by the investigator or qualified designee and found to be acceptable prior to each dose of trial treatment.

Protocol Version: 04/10/2019

Page 41 of 72

^{*}A pre-labeled box and shipping label will be provided.

Protocol Version: 04/10/2019 Page 42 of 72

Table 5 Laboratory Tests

Hematology	Chemistry	Urinalysis	Other
Hematocrit	Albumin	Blood	Serum β-human chorionic gonadotropin†
Hemoglobin	Alkaline phosphatase	Glucose	(β-hCG)†
Platelet count	Alanine aminotransferase (ALT)	Protein	Thyroid stimulating hormone (TSH)
WBC (total and differential)	Aspartate aminotransferase (AST)	Specific gravity	Total thriiodothyronine (T3) (If TSH abnormal)
Red Blood Cell Count	Lactate dehydrogenase (LDH)	Microscopic exam (If abnormal)	Free thyroxine (T4) (If TSH abnormal)
Absolute Neutrophil Count	Carbon Dioxide	results are noted	
Absolute Lymphocyte Count	(CO ₂ or biocarbonate)	Urine pregnancy test †	
	Uric Acid		
	Calcium		
	Chloride		Blood for correlative studies
	Glucose		
	Potassium		
	Sodium		
	Total Bilirubin		
	Direct Bilirubin (If total bilirubin is elevated above the upper limit of normal)		
	Total protein		
	Blood Urea Nitrogen		

Protocol Version: 04/10/2019

Page 43 of 72

8.1.3 Other Procedures

8.1.3.1 Withdrawal/Discontinuation

When a subject discontinues/withdraws prior to trial completion, all applicable activities scheduled for the final trial visit should be performed at the time of discontinuation. Any adverse events which are present at the time of discontinuation/withdrawal should be followed in accordance with the safety requirements. Subjects who a) attain a CR or b) complete 24 months of treatment with pembrolizumab may discontinue treatment with the option of restarting treatment if they meet the criteria. After discontinuing treatment following assessment of CR, these subjects should return to the site for a Safety Follow-up Visit and then proceed to the Follow-Up Period of the study.

8.1.3.2 Follow-up Visits

Subjects who discontinue trial treatment for a reason other than disease progression will move into the Follow-Up Phase and should be assessed every 12 weeks (90 ± 7 days) by radiologic imaging to monitor disease status. Every effort should be made to collect information regarding disease status until the start of new anti-neoplastic therapy, disease progression, death, end of the study or if the subject begins retreatment with pembrolizumab. Information regarding post-study anti-neoplastic treatment will be collected if new treatment is initiated.

Subjects who are eligible to receive retreatment with pembrolizumab will move from the follow-up phase to the Second Course Phase when they experience disease progression.

8.1.3.3 Second Course Phase (Retreatment Period)

Subjects who stop pembrolizumab with SD or better may be eligible for up to one year of additional pembrolizumab therapy if they progress after stopping study treatment. This retreatment is termed the Second Course Phase of this study and is only available if the study remains open and the subject meets the following conditions:

• Either

- Stopped initial treatment with pembrolizumab after attaining an investigatordetermined confirmed CR according to RECIST 1.1, and
 - Was treated for at least 24 weeks with pembrolizumab before discontinuing therapy
 - Received at least two treatments with pembrolizumab beyond the date when the initial CR was declared

OR

o Had SD, PR or CR and stopped pembrolizumab treatment after 24 months of study therapy for reasons other than disease progression or intolerability

AND

- Experienced an investigator-determined confirmed radiographic disease progression after stopping their initial treatment with pembrolizumab
- Did not receive any anti-cancer treatment since the last dose of pembrolizumab
- Has a performance status of 0 or 1 on the ECOG Performance Scale
- Demonstrates adequate organ function as detailed in Section 5.1.2
- Female subject of childbearing potential should have a negative serum or urine pregnancy test within 72 hours prior to receiving retreatment with study medication.
- Female subject of childbearing potential should be willing to use 2 methods of birth control or be surgically sterile, or abstain from heterosexual activity for the course of the study through 120 days after the last dose of study medication (Reference Section 5.7.2). Subjects of child bearing potential are those who have not been surgically sterilized or have been free from menses for > 1 year.
- Male subject should agree to use an adequate method of contraception starting with the first dose of study therapy through 120 days after the last dose of study therapy.
- Does not have a history or current evidence of any condition, therapy, or laboratory abnormality that might interfere with the subject's participation for the full duration of the trial or is not in the best interest of the subject to participate, in the opinion of the treating investigator.

Subjects who restart treatment will be re-treated at the same dose and dose interval as when they last received pembrolizumab. Treatment will be administered for up to one additional year. EDP1503 will also be restarted pending availability of supplement supply.

Visit requirements are outlined in Section 6.0 – Trial Flow Chart.

8.2 Assessing and Recording Adverse Events

An adverse event is defined as any untoward medical occurrence in a patient or clinical investigation subject administered a pharmaceutical product and which does not necessarily have to have a causal relationship with this treatment. An adverse event can therefore be any unfavorable and unintended sign (including an abnormal laboratory finding, for example), symptom, or disease temporally associated with the use of a medicinal product or protocol-specified procedure, whether or not considered related to the medicinal product or protocol-specified procedure. Any worsening (i.e., any clinically significant adverse change in

frequency and/or intensity) of a preexisting condition that is temporally associated with the use of the Merck's product, is also an adverse event.

Changes resulting from normal growth and development that do not vary significantly in frequency or severity from expected levels are not to be considered adverse events. Examples of this may include, but are not limited to, teething, typical crying in infants and children and onset of menses or menopause occurring at a physiologically appropriate time.

Merck product includes any pharmaceutical product, biological product, device, diagnostic agent or protocol-specified procedure, whether investigational (including placebo or active comparator medication) or marketed, manufactured by, licensed by, provided by or distributed by Merck for human use.

Adverse events may occur during the course of the use of Merck product in clinical trials, or as prescribed in clinical practice, from overdose (whether accidental or intentional), from abuse and from withdrawal.

Progression of the cancer under study is not considered an adverse event.

All adverse events will be recorded from first day of study drug administration through 30 days following cessation of treatment and at each examination on the Adverse Event case report forms/worksheets.

8.2.1 Definition of an Overdose for This Protocol and Reporting of Overdose to the Principal Investigator, Merck and Evelo

For purposes of this trial, an overdose of pembrolizumab will be defined as any dose of 1,000 mg or greater (≥5 times the indicated dose). No specific information is available on the treatment of overdose of pembrolizumab. Appropriate supportive treatment should be provided if clinically indicated. In the event of overdose, the subject should be observed closely for signs of toxicity. Appropriate supportive treatment should be provided if clinically indicated.

Overdose of EDP1503 will be defined as more than 6 capsules in a day. There is no known safety issue surrounding this however pill counts will be documented to confirm appropriate dosing. Appropriate supportive treatment should be provided if clinically indicated. Overdose of EDP1503 does not require report as a serious adverse event but will be reported as an adverse event.

If an adverse event(s) is associated with ("results from") the overdose of a Merck product, the adverse event(s) is reported as a serious adverse event, even if no other seriousness criteria are met.

If a dose of Merck's product meeting the protocol definition of overdose is taken without any associated clinical symptoms or abnormal laboratory results, the overdose is reported as a non-serious Event of Clinical Interest (ECI), using the terminology "accidental or intentional overdose without adverse effect."

All reports of overdose with and without an adverse event must be reported within 24 hours of site knowledge of the event to the UC CCC Cancer Clinical Trials Office and Lead Principal Investigator and within 2 working days hours to Merck Global Safety. (Attn: Worldwide Product Safety; [contact])

8.2.2 Reporting of Pregnancy and Lactation to the Principal Investigator and to Merck

Although pregnancy and lactation are not considered adverse events, it is the responsibility of investigators or their designees to report any pregnancy or lactation in a subject (spontaneously reported to them), including the pregnancy of a male subject's female partner that occurs during the trial or within 120 days of completing the trial completing the trial, or 30 days following cessation of treatment if the subject initiates new anticancer therapy, whichever is earlier. All subjects and female partners of male subjects who become pregnant must be followed to the completion/termination of the pregnancy. Pregnancy outcomes of spontaneous abortion, missed abortion, benign hydatidiform mole, blighted ovum, fetal death, intrauterine death, miscarriage and stillbirth must be reported as serious events (Important Medical Events). If the pregnancy continues to term, the outcome (health of infant) must also be reported.

Such events must be reported within 24 hours of site knowledge of the event to the UC CCC Cancer Clinical Trials Office and Lead Principal Investigator and within 2 working days to Merck Global Safety. (Attn: Worldwide Product Safety; [contact])

8.2.3 Immediate Reporting of Adverse Events to the Principal Investigator and to Merck

8.2.3.1 Serious Adverse Events

A serious adverse event is any adverse event occurring at any dose or during any use of Merck's product that:

- Results in death;
- Is life threatening;
- Results in persistent or significant disability/incapacity;
- Results in or prolongs an existing inpatient hospitalization;
- Is a congenital anomaly/birth defect;
- Is a new cancer (that is not a condition of the study);
- Is associated with an overdose;
- Is an other important medical event

Refer to Table 6 for additional details regarding each of the above criteria.

Any serious adverse event, or follow up to a serious adverse event, including death due to any cause other than progression of the cancer under study that occurs to any subject from first day of study drug administration through 90 days following cessation of treatment, or the initiation of new anti-cancer therapy, whichever is earlier, whether or not related to Merck or Evelo product, must be reported within 24 hours of site knowledge of the event to the UC CCC

Cancer Clinical Trials Office and Lead Principal Investigator and within 2 working days to Merck and Sarah Cannon Development Innovation Safety Department who will hold the Global Safety Database for EDP1503.

Non-serious Events of Clinical Interest will be forwarded to Merck and Sarah Cannon Development Innovation Safety Department and will be handled in the same manner as SAEs.

Additionally, any serious adverse event, considered by an investigator to be related to Merck product that is brought to the attention of the investigator at any time outside of the time period specified in the previous paragraph also must be reported immediately to the UC CCC Cancer Clinical Trials Office and Principal Investigator and to Merck and Evelo.

SAE reports and any other relevant safety information are to be forwarded to the Merck Global Safety [contact] and to Sarah Cannon Development Innovation Safety Department [contact].

All subjects with serious adverse events must be followed up for event outcome.

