5.2.1.2 Dose Modification (Escalation/Titration/Other)

Adverse events (both non-serious and serious) associated with pembrolizumab (or in combination with EDP1503) exposure may represent an immunologic etiology. These adverse events may occur shortly after the first dose or several months after the last dose of treatment. Pembrolizumab and EDP1503 must be withheld for drug-related toxicities and severe or life-threatening AEs. Supportive care guidelines, including use of corticosteroids are described below.

All Grade 3-5 adverse events considered possibly, probably or definitely related to study agent(s) must be discussed with the Lead Principal Investigator. All treating clinicians involved in the protocol are welcomed to discuss complicated cases at any time with the Lead Principal Investigator:

[name] University of Chicago Comprehensive Cancer Center [contact]

> Protocol Version: 04/10/2019 Page 21 of 72

Table 3 Dose Modification Guidelines (for both Pembrolizumab and EDP1503) for Drug-Related Adverse Events

Toxicity	Hold Treatment For Grade	Timing for Restarting Treatment	Treatment Discontinuation
Diarrhea/Colitis	2-3	Toxicity resolves to Grade 0-1	Toxicity does not resolve within 12 weeks of last dose or inability to reduce corticosteroid to 10 mg or less of prednisone or equivalent per day within 12 weeks
	4	Permanently discontinue	Permanently discontinue
AST, ALT, or	2	Toxicity resolves to Grade 0-1	Toxicity does not resolve within 12 weeks of last dose
Increased Bilirubin	3-4	Permanently discontinue (see exception below) ^a	Permanently discontinue
Type 1 diabetes mellitus (if new onset) or Hyperglycemia	T1DM or 3-4	Hold pembrolizumab for new onset Type 1 diabetes mellitus or Grade 3-4 hyperglycemia associated with evidence of beta cell failure	Resume pembrolizumab when patients are clinically and metabolically stable
Hypophysitis	2-4	Toxicity resolves to Grade 0-1. Therapy with pembrolizumab can be continued while endocrine replacement therapy is instituted	Toxicity does not resolve within 12 weeks of last dose or inability to reduce corticosteroid to 10 mg or less of prednisone or equivalent per day within 12 weeks
Hyperthyroidism	3	Toxicity resolves to Grade 0-1	Toxicity does not resolve within 12 weeks of last dose or inability to reduce corticosteroid to 10 mg or less of prednisone or equivalent per day within 12 weeks
	4	Permanently discontinue	Permanently discontinue

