5.8 Subject Withdrawal/Discontinuation Criteria

Subjects may withdraw consent at any time for any reason or be dropped from the trial at the discretion of the investigator should any untoward effect occur. In addition, a subject may be withdrawn by the investigator or the Principal Investigator if enrollment into the trial is inappropriate, the trial plan is violated, or for administrative and/or other safety reasons. Specific details regarding discontinuation or withdrawal are provided in Section 7.1.4 – Other Procedures.

Definition of Dose Limiting Toxicity: Any toxicity of >=Grade 3, any autoimmune toxicity >CTCAE Gr 2; DLT observation period is for the length of monotherapy for each cohort.

A subject must be discontinued from the trial for any of the following reasons:

- The subject or legal representative (such as a parent or legal guardian) withdraws consent.
- Confirmed radiographic disease progression

Note: A subject may be granted an exception to continue on treatment with confirmed radiographic progression if clinically stable or clinically improved.

- Unacceptable adverse experiences as described in Section 5.2.1.2
- Intercurrent illness that prevents further administration of treatment
- Investigator's decision to withdraw the subject
- The subject has a confirmed positive serum pregnancy test
- Noncompliance with trial treatment or procedure requirements
- The subject is lost to follow-up
- Completed 24 months of uninterrupted treatment with pembrolizumab or 35 administrations of study medication, whichever is later.

Note: 24 months of study medication is calculated from the date of first dose. Subjects who stop pembrolizumab after 24 months may be eligible for up to one year of additional study treatment if they progress after stopping study treatment provided they meet the requirements.

Administrative reasons

After the end of treatment, each subject will be followed for 30 days for adverse event monitoring (serious adverse events will be collected for 90 days after the end of treatment). Subjects who discontinue for reasons other than progressive disease will have post-treatment follow-up for disease status until disease progression, initiating a non-study cancer treatment, withdrawing consent or becoming lost to follow-up. After documented disease progression each subject will be followed by telephone for overall survival until death, withdrawal of consent, or the end of the study, whichever occurs first.

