- c Patients who discontinue treatment without progression will have follow up visits for up to 2 years following drug discontinuation
- d Archival tissue for newly diagnosed metastatic melanoma is allowed in cohort 1. Fresh biopsies are otherwise required. Second biopsy at the end of the EDP1503 run-in period after at least 10 days in cohort 1 and at least 4 days in cohort 2.
- e Samples to be collected for correlative blood analysis are detailed in section 8.1.1.11
- f Sample to be taken prior to the initiation of pembrolizumab therapy
- g Nursing assessment for adverse events at 48 hours which can be completed by telephone.
- h Research cytokines, blood culture, whole blood

Protocol Version: 04/10/2019

Page 35 of 72

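### The SAE windows in 5.8 and 8.2.3.1 conflict, patients who progress have no scheduled safety contact after the 30-day visit, and serious screening-biopsy complications have no clear reporting duty

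*Combined protocol and SAP*

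**What the plan says.** **End of the window.** Section 5.8: "serious adverse events will be collected for 90 days after the end of treatment". Section 8.2.3.1 sets all-cause SAE reporting "from first day of study drug administration through 90 days following cessation of treatment, or the initiation of new anti-cancer therapy, whichever is earlier". Section 8.2, for adverse events in general: "All adverse events will be recorded from first day of study drug administration through 30 days following cessation of treatment". Neither 5.8 nor 8.2 ends safety capture when a new cancer treatment begins.

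**Outside the window.** Section 8.2.3.1 also requires immediate reporting of an SAE that the investigator considers "related to Merck product that is brought to the attention of the investigator at any time outside of the time period" just defined. No equivalent sentence names Evelo product.

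**Contact after treatment.** The flow chart in 6.1 has a safety visit 30 days after discontinuation, then 12-weekly visits only for patients without progression; 8.1.3.2 says the same. Section 8.1.1.5.3 brings the 30-day visit forward if new therapy starts sooner, and then moves the patient to survival follow-up. For patients who progress, 5.8 says: "After documented disease progression each subject will be followed by telephone for overall survival". It gives no interval and no safety content.

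**Start of the window.** Sections 8.2 and 8.2.3.1 both begin at first study drug. Yet 8.2 defines an adverse event to include one "temporally associated with the use of a medicinal product or protocol-specified procedure", and the flow chart marks adverse event review at screening. On baseline tissue, footnote d of the flow chart accepts archival tissue for newly diagnosed metastatic disease in Cohort 1 and adds: "Fresh biopsies are otherwise required". Section 4.2.3.2 is wider: it accepts earlier core or surgical tissue if no systemic treatment came in between, and does not limit this to one cohort.

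**The concern.** Section 5.2.1.2 says of immune-related events: "These adverse events may occur shortly after the first dose or several months after the last dose of treatment". Late events are therefore expected, and the second secondary objective in 3.2 is to show that the combination has a safety profile similar to pembrolizumab alone. If all-cause SAE reporting stops when a patient switches treatment, and patients who progress are not asked about safety after the 30-day visit, late events will be found least reliably in the patients who progress and switch. The combination could then look safer late on than it is.

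The reporting tail has a specific weakness. EDP1503 is the agent under test, but the open-ended clause is tied to the other drug. It also depends on the event reaching the investigator unprompted, and on attribution to pembrolizumab after another therapy has begun.

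At the start of the window, a fresh baseline biopsy is a risk that the trial itself imposes on some patients. Its serious complications should have an unambiguous route into the trial record.

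**Working it through.** The plan states no figure on this point, so the check compares the sections and uses day arithmetic only.

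**1. SAE window.** Let T be the day, counted from the end of treatment, on which new anti-cancer therapy starts. The values of T are assumptions, because the documents give no distribution for it.

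- All-cause reporting window in 8.2.3.1 = min(T, 90) days.
- Collection window in 5.8 = 90 days.
- Shortfall = 90 − min(T, 90).

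| T | Window, 8.2.3.1 | Window, 5.8 | Shortfall |
|---|---|---|---|
| 14 | 14 | 90 | 76 |
| 30 | 30 | 90 | 60 |
| 60 | 60 | 90 | 30 |
| 90 or later | 90 | 90 | 0 |

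**2. Against the window for all adverse events.** Section 8.2 runs to day 30 whatever T is. For any T below 30, all-cause SAE reporting closes before recording of non-serious events does. With T = 10, a hospitalization on day 20 is still recorded under 8.2, and 8.2.4 still requires it to be assessed for seriousness. What 8.2.3.1 no longer requires is its expedited all-cause report.

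**3. Scheduled contact.**

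- Patients who progress: after the day-30 visit there is no scheduled safety contact to day 90, which is 90 − 30 = 60 days. If new therapy starts before day 30, the last safety visit is earlier still.
- Patients who do not progress: the next visit is at 12 × 7 = 84 days by the flow chart, or at 90 ± 7 = 83 to 97 days by 8.1.3.2. They too have a long interval, and their visit may fall after day 90, but they do have a later scheduled review of adverse events.

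**4. Out-of-window clause.** Of three kinds of SAE after a switch:

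- related to pembrolizumab: reportable at any time, if the investigator hears of it;
- attributed only to EDP1503: not covered by this clause;
- not attributed to either drug: not covered by this clause.

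**5. Biopsies.**

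- Post-run-in biopsy: taken after EDP1503 has started, so inside both windows.
- Baseline biopsy: taken before first study drug, so before both windows open. It applies only to patients without acceptable prior tissue, and 4.2.3.2 and footnote d differ on who those are.

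**The case against.** Four arguments on the other side carry weight.

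**Two duties rather than one.** Section 8.2.3.1 sits under immediate reporting, while 5.8 speaks of collection, so the narrower clause need not cancel the wider one. This is a fair reading, and it is why the shortfall above cannot be called data lost. It does not settle the matter, because no other section says how SAEs are to be collected on days 31 to 90.

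**Other safeguards.** Section 8.2.5 asks for expedited reporting of SAEs on the study without repeating the cut-off, and requires unexpected adverse reactions to go to the IND holder. Section 8.2.3.3 ties reactions to the study agent, so that route is not confined to Merck product. Section 8.1.1.6 has adverse events recorded through follow-up and assessed as the flow chart specifies, which includes screening. These provisions narrow the gap. But 8.2.5 sets no collection window of its own, its second route covers only unexpected reactions, and neither section schedules contact for patients who progress. Section 8.1.1.6 also conflicts with the start and end dates in 8.2.

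**The cut-off may be deliberate.** Section 8.1.1.5.3 brings the safety visit ahead of new therapy, and 8.2.2 shortens pregnancy reporting once new therapy begins. Limiting contamination by the next drug is defensible. If that is the intention, 5.8 should say so. Section 8.2.2 also keeps 30 days after cessation, which 8.2.3.1 does not.

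**Limited analytic effect.** The Safety population needs at least one dose and the summaries in 10.1 are of treatment-emergent events, so pre-dose biopsy events would not enter those tables. Combination safety is tabulated without a formal comparison. All of this stands.

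A reader might go further and infer that most SAE data are lost for patients who switch, that nearly all of Cohort 2 is affected, or that biopsy harms go uncounted altogether. The documents support none of these. Events to day 30 are still recorded and assessed for seriousness. Non-responders include patients with stable disease, treatment past progression is allowed, and patients who stop for other reasons enter 12-weekly follow-up. The post-run-in biopsy lies inside the window.

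**Conclusion.** The concern holds as an inconsistency in the safety windows together with a gap in scheduled contact. Sections 5.8, 8.2 and 8.2.3.1 give different end points for SAEs. As 8.2.3.1 is written, three groups have no clear reporting duty: all-cause late SAEs after a switch of therapy, SAEs attributed only to EDP1503 after the window closes (apart from unexpected reactions that come to notice under 8.2.5), and serious complications of a fresh baseline biopsy. Patients who progress have 60 days, from 31 to 90, without a scheduled safety contact.

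That figure measures time without contact, not events missed. The number of SAEs missed cannot be estimated, because the documents give neither the timing of new therapy nor a late SAE rate. The effect falls on late safety of the combination, a secondary objective, and on oversight of screening procedures. The co-primary run-in safety endpoint is unaffected. The point should be acted on, but it does not threaten the trial's primary conclusions.

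**What to change.** 1. Reconcile 5.8, 8.2 and 8.2.3.1 to a single SAE window, keeping the 90-day collection of 5.8 for every patient. Record the start date of new anti-cancer therapy and flag later events instead of ending collection. Extend the clause for related SAEs outside the window to Evelo product.
2. Date the survival call already planned for patients who progress at about day 90, and add questions on SAEs and immune-related events.
3. Record and report SAEs related to protocol-mandated screening procedures from consent, listed separately from treatment-emergent events. Align 4.2.3.2 with footnote d of the flow chart, so that it is clear who needs a fresh baseline biopsy.

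The cost is protocol and case report form wording, plus a date and a few questions for a call that is already planned. The downside is that some SAEs caused by the next therapy will be collected; the flag allows them to be shown separately.
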